5 NCT04907903
6
7 Version: 02/02/2022
8
9
10
11
12
13
14
15
16
17
18
19
20
21
22
23
24
25
26

27 **ABSTRACT**

28 **Background** This study aims to evaluate the feasibility and effectiveness of the RinasciMENTE
29 program, an Internet-based self-help intervention based on Cognitive Behavioral Therapy (CBT)
30 principles and techniques in supporting individuals experiencing psychological impairments during
31 the COVID-19 pandemic. A randomized controlled trial (RCT) design with random allocation at the
32 level of individual will be conducted to compare the impact of the RinasciMENTE program with a
33 waiting list control in improving the psychological functioning of the general population during the
34 COVID-19 pandemic.

35 **Methods** A minimum sample of 128 participants experiencing mild/subthreshold levels of
36 psychological symptoms during the COVID-19 pandemic will be recruited. After the initial
37 screening, participants will be randomly assigned to either the experimental group or the control
38 condition. The program will last 2 months, during which participants will receive 8 weekly CBT
39 treatment modules. The impact of the RinasciMENTE program on selected primary and secondary
40 psychological outcomes will be tested at the end of the intervention (2 months), 6- and 12-month
41 follow-up.

42 **Discussion** We expect people to show an increased level of psychological functioning, and to acquire
43 the skills and self-confidence necessary to deal with the psychological consequences of the COVID-
44 19 outbreak and its related social isolation during and following the pandemic.

45 **Trial registration** ClinicalTrials.gov NCT0497903 Registered on 28 May 2021.

46

47 *Keywords:* COVID-19, Internet-based intervention, Self-help, Cognitive-behavioral therapy,
48 Psychological distress, Randomized controlled trial, Clinical psychology.

49

50

51

52

53 **BACKGROUND**

54 In the hope of reducing the transmission of Coronavirus Disease 2019 (COVID-19) governments
55 around the world have implemented unprecedentedly strict preventive measures, such as home
56 confinement, mobility restrictions, and social distancing (1, 2). However, the COVID-19 pandemic
57 and the resulting economic recession (3) have negatively affected the mental health of many people
58 (4). The most common mental disorders emerging were anxiety and depression, obsessive-
59 compulsive symptoms, insomnia, and post-traumatic stress disorder symptoms (5-9). These were not
60 only a direct consequence of the pandemic but also largely driven by the effects of prolonged social
61 isolation. Although necessary to limit the spread of the epidemic, social isolation resulted in increased
62 sedentary lifestyle (2) and other COVID-19-related stressors including fears of infection, frustration
63 and boredom, and lack of in-person contacts (10, 11). Italy was one of the most affected countries
64 during the outbreak, initially accounting for over 223.000 infected individuals and more than 31.000
65 deaths (12). In May 2021, 4.111.110 people resulted having contracted the virus, and 122.833 of them
66 died as a consequence (13, 14).

67 In this scenario, it is crucial to assess the level of psychological distress and to provide ad hoc
68 psychological interventions to support the individuals' wellbeing in both the general population (15,
69 16) and at-risk groups (17, 18) during the COVID-19 pandemic.

70 Accordingly, evidence from previous epidemics highlights the risk for long-term mental health issues
71 (19) and emphasizes the need for continued support during and after the pandemic (20).

72 Many health organizations have already committed resources to support the mental well-being of the
73 individuals, adapting existing standard programs to meet evolving demands caused by COVID-19
74 (21). In this regard, cognitive-behavioral techniques including restructuring of cognitive bias, as well
75 as activity planning and relaxation, have been shown particularly useful in addressing psychological
76 distress (22-25).

77 Cognitive-behavioral therapy (CBT) is a time-sensitive, structured, present-oriented psychotherapy
78 aimed at helping people identify and change thinking and behavior patterns that are harmful or
79 ineffective, replacing them with more accurate thoughts and functional behaviors.

80 Still, given that face-to-face treatment is not always viable in these circumstances (26) a new way to
81 deliver psychological treatments is urgently required, and a potentially practical solution is to deliver
82 therapy remotely (14, 27-30).

83 Many systematic reviews and randomized controlled trials (RCTs) demonstrated the utility and the
84 efficacy of Internet-based interventions in supporting people experiencing psychological problems
85 (31-33).

86 Advantages include improved access for individuals (26) who have variable schedules, an important
87 workload, or who are afraid of being contaminated through face-to-face contacts (34-36), as well as
88 cost-effectiveness compared to face-to-face treatment.

89 Due to its features, CBT well-suits many aspects of distance therapy. First, it is a talking therapy, and
90 this aspect can be relatively easily retained remotely. It also emphasizes the importance of the person
91 making changes and working on specific tasks between sessions to bring about the change (37); this
92 is perfectly consistent with working remotely. Moreover, with distance therapy, the patient may be
93 less likely to attribute the progress to the therapist and more likely to have an improved sense of self-
94 efficacy (38). One of the goals of CBT is to "become your therapist" by learning skills people can use
95 on their own after treatment to keep feeling well.

96 Research shows that CBT delivered digitally (iCBT) is effective in reducing symptoms of social
97 anxiety disorder (39, 40), generalized anxiety disorder (41, 42), panic disorder (43), major depressive
98 disorder (44-46), obsessive-compulsive disorder (47) and insomnia (48) in both guided and unguided
99 self-help programs. Specifically, a review of 30 studies found that CBT-based self-help interventions
100 significantly reduced both anxiety and depression. Studies also show that people tend to maintain
101 their progress over time, which is very encouraging (49). Furthermore, since patients can return to

102 the program at their convenience to access treatment information, this may facilitate learning and
103 retention.

104 Despite a growing interest in the field of web-based psychological interventions, Internet-based CBT
105 self-help programs remain underdeveloped.

106 To fill this important gap in the literature and to properly meet the need of the population, it is crucial
107 to promote and investigate the impact of this Internet-based psychological intervention in increasing
108 individuals' emotional well-being.

109 For this reason, the present RCT aims to explore the effectiveness of a novel Internet-based CBT self-
110 help program specifically developed to address the immediate stress and prevent long-term
111 psychological consequences of the COVID-19 pandemic among Italians both living in the county and
112 abroad. To assess its impact, the effects of the RinasciMENTE program will be compared with a
113 waiting list (WL) condition on selected self-reported measures immediately following the 8-week
114 intervention and at 6- and 12-month follow-up.

115 The primary hypothesis that will be tested is that the program will be feasible and effective in
116 increasing the psychological functioning of the person.

117 The secondary hypothesis will test whether participants assigned to the experimental condition will
118 show a reduced level of stress, anxiety, depression, and fear of COVID-19, as well as improved
119 emotion regulation strategies, self-efficacy, and psychological well-being than those in the WL
120 condition at treatment termination.

121 Moreover, participants in the experimental condition will be expected to present maintained outcomes
122 or further decreased psychological symptoms at 6 and 12-month after the end of the treatment
123 program.

124 **METHODS**

125 **Design**

126 The project consists of a prospective, randomized, open, and parallel group-controlled study with two
127 arms: an experimental arm with 8 online weekly CBT self-help sessions, and a waiting list (WL)
128 control arm.

129 **Ethical Statement**

130 The study was approved by the Ethical Committee of the Catholic University of Milan, Italy (ID: 25-
131 21). All procedures performed in the study will be run following the ethical standards of the
132 institutional and/or national research committee and with the Helsinki Declaration and its later
133 amendments or comparable ethical standards.

134 **Patients and public involvement**

135 Participants from the general population will be recruited through advertisements placed on social
136 media platforms (i.e., Facebook, Instagram, Twitter), and online webinars on the topic.
137 The recruitment materials will include details about the study aim, the treatment delivered, and the
138 conditions for participation, together with the weblink to access the program.

139 Inclusion criteria for the participants into the study will be: (A) being fluent in the Italian language;
140 (B) being over 18 years old; (C) providing online informed consent; and (D) showing
141 mild/subthreshold levels of symptoms at the 12-Item General Health Questionnaire (GHQ-12) -
142 Italian version (50, 51) - the most extensively used screening tool assessing the severity of common
143 mental disorders over the past few weeks using a 4-point Likert-type scale (from 0 to 3). Its total
144 score ranges from 0 to 36, with high scores indicating worse health status. Only participants who
145 score ≥ 15 on the GHQ and show moderate levels of symptoms at the clinical interview will be
146 included in the study.

147 Participants will be excluded from the program if: (A) presenting visual, hearing, or cognitive
148 impairments that will prevent them from receiving and following the intervention; (B) suffering from
149 severe psychiatric disorders according to the Diagnostic and Statistical Manual of Mental Disorders
150 (DSM 5) (52); (C) lacking basic computer skills or internet access.

151 Respondents will not be excluded if already receiving psychopharmacological therapy or
152 psychological-psychotherapeutic support.

153 **Sample size calculation**

154 The minimum sample size required to conduct this study was calculated using an a priori sample size
155 calculator (G*Power 3.1.9.2 software) for *F* tests (53-55). Participants were randomly divided into
156 two groups: (A) iCBT self-help and (B) waiting list control. Moreover, participants will be measured
157 in 3 moments: (1) before the intervention, (2) at the end of intervention (two months later), and (3)
158 after 12 months from treatment termination. Due to the novelty of the study from which to derive
159 realistic estimates of effect sizes, the partial η^2 was set a priori to assume a value of 0.02 – small
160 effect size (56, 57) – which provides a Cohen's *f* value of 0.143. Moreover, the type I error (α) rate
161 was set at 0.05 (two-sided) and the Power ($1 - \beta$) was set at 0.95, and the a priori correlation between
162 repeated measures was set at 0.50, according to general guidelines (56). Lastly, the non-sphericity
163 correction was set to 1. Results showed that there is a 95% chance of correctly rejecting the null
164 hypothesis of no significant effect of the interaction with 128 participants in total (64 for each group).

165 **Randomization and blinding**

166 The random randomization scheme will be generated using the Web site Randomization.com (58).
167 Allocation concealment will be ensured by the program generating an anonymous code for each
168 participant that will be associated with the randomization sequence. Due to the nature of the
169 intervention, the treatment group allocation cannot be concealed from the participants, nor the
170 research team and assessor of outcomes. Participants will be assigned to one of two conditions within
171 2 working days from their baseline assessment (Figure 1).

172

173 *** PLEASE INSERT Figure 1: Flow chart of the RinasciMENTE study

174 **Measures**

175 *Demographic and clinical information.* Information about age, gender, education, civil status, weight, and
176 high - used to calculate the Body Mass Index (BMI, kg/m²) in presence of dysfunctional eating behaviors
177 - will be self-reported online at baseline. Subjects will be also asked to provide information about the
178 country where they are currently living, their work situation (before and after the COVID-19 pandemic),
179 and the personal experience they made of both COVID-19 pandemic and related preventive measures.
180 The Italian version of the following psychological measures will be also collected at baseline (T0),
181 treatment termination after 2 months (T1), at 6-month (T2), and 12-month (T3) follow-up in the
182 experimental condition only). Please see Figure 2 for a detailed project timeline.

183 *** INSERT GANTT Figure 2: Gant of the RinasciMENTE study

184 Primary outcome:

185 *Outcome Questionnaire (OQ-45)* (59) composed by 45 items rated on a 5-point Likert scale (0 = Never –
186 4 = Almost always) assessing the treatment progresses across 3 different domains: Symptom Distress (SD
187 – 25 items: 2, 3, 5, 6, 8, 9, 10, 11, 13, 15, 22, 23, 24, 25, 27, 29, 31, 33, 34, 35, 36, 40, 41, 42 and 45),
188 Interpersonal Relations (IR – 11 items: 1, 7, 16, 17, 18, 19, 20, 26, 30, 37 and 43), and Social Role (SR –
189 9 items: 4, 12, 14, 21, 28, 32, 38, 39 and 44). The OQ-45 total score is calculated by summing the score of
190 the three subscales. Total score (range 0 to 180) is calculated by the sum of the items.

191 *Secondary outcomes:*

192 *Perceived stress scale* (PSS) (60), composed of 10 items rated on a 5-point Likert scale (from 0 = never to
193 4 = very often) assessing the degree to which situations in one's life are appraised as stressful. PSS scores
194 are obtained by reversing responses (i.e., 0 = 4, 1 = 3, 2 = 2, 3 = 1 and 4 = 0) to the four positively stated
195 items (items 4, 5, 7, and 8) and then summing across all scale items. The total score (range 0 to 40) is
196 calculated by the sum of the items.

197 *Emotional regulation questionnaire (ERQ)* (61), composed of 10 items rated on a 7-point Likert scale
198 (from 1 = strongly disagree to 7 = strongly agree) assessing respondents' tendency to regulate their

199 emotions in two ways: Cognitive Reappraisal (items 1, 3, 5, 7, 8, and 10) and Expressive Suppression
200 (items 2, 4, 6, and 9). The total score (range 7 to 70) is calculated by the sum of the items.

201 *Depression Anxiety Stress Scales-Short Version* (DASS-21) (62), composed by 21 statements rated on a
202 4-point Likert scale (from 0 = did not apply to me at all to 3 = applied to me very much) assessing the
203 negative emotional states of depression, anxiety, and stress. Each of the three DASS-21 scales contains 7
204 items: *Depression*: dysphoria, hopelessness, devaluation of life, self-deprecation, lack of
205 interest/involvement, anhedonia, and inertia - (Items 3, 5, 10, 13, 16, 17, and 21); *Anxiety*: autonomic
206 arousal, skeletal muscle effects, situational anxiety, and subjective experience of anxious affect -
207 (Items 2, 4, 7, 9, 15, 19, and 20); *Stress*: levels of chronic nonspecific arousal, difficulty relaxing,
208 nervous arousal, and being easily upset/agitated, irritable/over-reactive and impatient - (Items 1, 6, 8,
209 11, 12, 14, and 18). Sum scores are computed by adding up the scores on the items per (sub)scale and
210 multiplying them by 2. Sum scores for the total DASS-total scale thus range between 0 and 126, and
211 those for each of the subscales may range between 0 and 42. Ranges of scores correspond to levels
212 of symptoms, ranging from “normal” to “extremely serious”. Notably, the DASS-21 has been recently
213 used to investigate the impact of the COVID-19 pandemic on the physical and mental health of
214 different populations worldwide (63-65).

215 *Fear of COVID-19 Scale* (FCV-19S) (66) composed by 7-item rated on a 5-point scale, ranging from 1
216 (from 1 = strongly disagree to 5 = strongly agree) reflecting cognitive, emotional, behavioral, and
217 physiological manifestations of fear related to COVID-19. The total score (range 7 to 35) is calculated by
218 the sum of the items. All items are positively worded, implying that higher scores indicate greater levels of
219 fear.

220 *General Self-efficacy Scale* (GSES) (67), composed of 10 items rated on a 4-point Likert scale (from
221 1 = Not at all true to 4 = exactly true) assessing the individuals’ confidence in their ability to cope
222 with a variety of difficult or stressing situations. The total score is calculated by finding the sum of

223 all items. For the GSE, the total score ranges between 10 and 40, with a higher score indicating more
224 self-efficacy.

225 *World Health Organization Quality of Life (WHOQOL)-BREF* (68), composed of 26 items rated on
226 a 5-point Likert scale assessing four domains: physical health (7 items on mobility, daily activities,
227 functional capacity, energy, pain, and sleep), psychological health (6 items on self-image, negative
228 thoughts, positive attitudes, self-esteem, mentality, learning ability, memory concentration, religion,
229 and the mental status), social relationships (3 items on personal relationships, social support, and sex
230 life), and environmental health (8 items related to financial resources, safety, health, and social
231 services); it also contains QOL and general health items. The scores (range 25 to 130) are transformed
232 linearly to a 0–100-scale.

233

234 Moreover, *adherence* will be measured through indicators such as the percentage of visited pages or the
235 number of accesses.

236 *Acceptability* will be assessed by registering the participants' attrition rates and – for the experimental
237 group only - by the use of the *System Usability Scale* (SUS)(69) composed of 10 statements scored
238 on a 5-point Likert scale (from 1 = strongly disagree to 5 = strongly agree). The final score range from
239 0 to 100, with a score above 68 indicating the absence of usability problems.

240

241 **Procedure**

242 Those interested in taking part in the program will be directed to the RinasciMENTE website
243 (<https://www.iterapi.se/sites/rinascimente/login>) where they will find the written (online) consent,
244 and after the acceptance of this, to each participant will be sent a document with information on the
245 aims and requirements of the study.

246 They will be first asked to complete the GHQ-12 self-report questionnaires. Then, during the
247 following 5 days, they will choose a time slot to be contacted for a clinical semi-structured interview

248 lasting about 45 minutes, led by a certified clinical psychotherapist not involved in the study who will
249 further assess the individual's eligibility to take part in the study. Additional information about the
250 study and the randomization procedure will be also given to all respondents.

251 Next, the inclusion of each participant in the study and modules comprising the program will be
252 discussed in a group by the professional who will conduct the interview and the research investigators

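### The 95% power at 128 participants belongs to a three-measurement interaction that the design cannot test; the planned T0–T1 comparison has no stated power and no dropout allowance

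*Combined protocol and SAP*

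**What the plan says.** The sample size section (Methods) describes two groups measured "in 3 moments: (1) before the intervention, (2) at the end of intervention (two months later), and (3") "after 12 months from treatment termination". On effect size, "the partial η^2 was set a priori to assume a value of 0.02 – small", which it converts to Cohen's f = 0.143. The other inputs are a two-sided alpha of 0.05, power of 0.95, a correlation of 0.50 between repeated measures and a non-sphericity correction of 1. The result is a 95% chance of rejecting the "hypothesis of no significant effect of the interaction with 128 participants in total (64 for each group"). The Abstract repeats the number: "A minimum sample of 128 participants experiencing mild/subthreshold levels of" psychological symptoms.

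Other sections describe a different comparison:

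- **Measures and Procedure:** both arms are assessed at baseline (T0) and at two months (T1). Only the experimental arm is assessed at 6 and 12 months (T2, T3).
- **Procedure:** the waiting list gets access to the programme after two months.
- **Statistical analysis:** the between-group repeated-measures ANOVA runs from baseline to treatment termination. A within-group ANOVA over all four time points follows, in the experimental arm only.
- **Background, hypotheses:** the secondary hypothesis compares the arms in the "condition at treatment termination" sense. Follow-up expectations concern the experimental condition only. The primary hypothesis names neither a comparator nor a time point.
- **Background, aims:** one sentence points the other way. "To assess its impact, the effects of the RinasciMENTE program will be compared with a" waiting list right after the "intervention and at 6- and 12-month follow-up".

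No dropout rate is given. The Statistical analysis section says that dropouts are excluded, and also that the comparison follows intention to treat. Expected results anticipates that dropout may exceed that of face-to-face therapy.

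**The concern.** The power statement is the only justification for 128, and it describes a test that needs 12-month data from both arms. The waiting list has none. Even if it were measured then, it would already have had access to the programme.

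A reader therefore cannot tell what difference at T1 the trial is powered to detect. The small-effect label does not help, because under this calculation it stands for a T1 difference above half a standard deviation on most plausible readings. In addition, 128 is the uninflated output of the calculation, so any exclusion of dropouts lowers the power further.

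**Working it through.** **Inputs from the sample size section:** partial η² = 0.02, alpha = 0.05, correlation ρ = 0.50, ε = 1, N = 128 in two equal groups. From these, f = √(0.02/0.98) = 0.1429.

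**Step 1: reproduce the stated figure.** For a within-between interaction with m measurements and two groups (G*Power default effect-size option):

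λ = f²·N·m/(1 − ρ), df1 = m − 1, df2 = (N − 2)(m − 1), noncentral F.

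- m = 3, N = 128: λ = 0.020408 × 128 × 3/0.5 = 15.67; F(2, 252); power 0.951.
- m = 3, N = 126: power 0.947.

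So 128 is exactly the three-measurement answer. The same inputs with m = 2 require 162, and with m = 4 require 108.

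**Step 2: the planned test, same f.** With m = 2 and N = 128, λ = 0.020408 × 128 × 2/0.5 = 10.45; F(1, 126); power 0.894. With two measurements f = D/4, where D is the between-group difference at T1 in SD units (no difference at baseline), so D = 4 × 0.1429 = 0.57.

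This depends on ρ. At the same f, power is 0.77, 0.83 and 0.95 for ρ = 0.3, 0.4 and 0.6.

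**Step 3: the planned test, with f keeping its three-measurement meaning.** Let the group differences at T0, T1 and 12 months be (0, D, rD). Then f = k·D with k = ½·√(mean of squared deviations of these differences, at D = 1, from their mean). For r = 1 the deviations are −2/3, 1/3, 1/3, so k = ½·√(2/9) = 0.2357 and D = 0.1429/0.2357 = 0.606. Power for T0–T1 uses λ = D²·N/(8(1 − ρ)), which is D²·N/4 at ρ = 0.50.

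| Course of the effect after T1 | r | D (SD) | T0–T1 power, N = 128 |
|---|---|---|---|
| Halves by 12 months | 0.5 | 0.70 | 0.976 |
| Persists | 1 | 0.61 | 0.925 |
| Grows by 25% | 1.25 | 0.53 | 0.844 |
| Grows by 50% | 1.5 | 0.46 | 0.73 |
| Doubles | 2 | 0.35 | 0.50 |

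Power for T0–T1 exceeds 0.95 only if between 12.5% and 87.5% of the T1 difference remains at 12 months.

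**Step 4: what 128 complete participants can detect.** At ρ = 0.50 the T0–T1 test has 80% power at D = 0.50 and 95% power at D = 0.64.

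**Step 5: dropout.** The documents give no rate, so these rates are assumptions, with equal loss in both arms and dropouts excluded.

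| Assumed loss (number analysed) | D = 0.53 | D = 0.57 | D = 0.61 | D = 0.70 |
|---|---|---|---|---|
| 10% (116) | 0.81 | 0.86 | 0.90 | 0.96 |
| 20% (102) | 0.75 | 0.82 | 0.86 | 0.94 |
| 30% (90) | 0.70 | 0.76 | 0.81 | 0.91 |

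At D = 0.57, power falls to 0.80 with 98 analysed, a loss of 30/128 = 23%. Under intention to treat with imputation, the documents do not determine the loss.

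**The case against.** The strongest reply is that little is lost in practice. On the two most natural readings, the same f or a persisting effect, power before dropout is 0.89 to 0.93. The protocol calls 128 a minimum, plans weekly reminders and allows imputation. All of this is true, and it limits the seriousness of the point. It does not supply a power statement for the planned test, and a minimum without a larger target is not a dropout allowance.

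The course of the effect is also not wholly open. The Background expects maintained or further reduced symptoms in the experimental arm. With a stable waiting list that means r ≥ 1 and T1 power of at most 0.925, so the halving case fits that expectation poorly. This weakens the most favourable figure in the table, and later growth beyond 25% would be worse than 0.84. A waiting list that improves once it has access could still produce r below 1.

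The SD figures also rest on the G*Power default effect-size option, which the protocol does not name. Under the SPSS-style option, partial η² = 0.02 needs 382 participants for three measurements. At 128 that option gives power of about 0.51 for three measurements and 0.36 for two, where the T1 difference is about 0.28 SD. Of the variants tried, only the default with three measurements yields 128, so it is evidently what was used. The qualification still belongs in the text.

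Finally, the aims sentence could be read as intending a 12-month comparison. One sentence cannot create control data that the schedule does not collect.

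**Conclusion.** The point stands. The calculation is numerically correct but describes a test that the schedule rules out and the analysis section does not plan. The planned T0–T1 comparison has no stated power. With 128 complete participants it is about 0.89 with the protocol's f carried over, and 0.84 to 0.98 if the effect grows by up to 25%, persists or halves by 12 months. It is lower if the effect builds later. Whether 95% is too high therefore depends on a pattern of means that the protocol does not specify.

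These figures assume ρ = 0.50, equal SDs across arms and times, and the default effect-size option. This is a defect in the justification that should be corrected; it does not show that the trial is badly underpowered.

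**What to change.** 1. Rewrite the sample size paragraph for two groups and two measurements (T0, T1), and remove the 12-month measurement from the power basis.
2. State the assumed T1 difference in SD units beside the small-effect label, together with ρ and the effect-size option used. Give the resulting power at 128 complete: for example, 89% at 0.57 SD and ρ = 0.50. If 95% is kept at 128, say that it corresponds to about 0.64 SD and justify that value.
3. State the power at a named, assumed dropout rate: for example, about 82% at 0.57 SD if 20% are lost and excluded.
4. Bring the aims sentence on waiting-list comparisons at 6 and 12 months into line with the hypotheses, the schedule and the analysis section. Clarify the Abstract's statement on follow-up testing in the same way.
5. Reconcile the exclusion of dropouts with intention to treat, so that the number analysed is defined.

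The cost is rewording; the planned between-group ANOVA is unchanged. No extra participants are needed if the sponsor accepts the power that 128 provides. Keeping both f = 0.143 and 95% power would need 162 complete participants, or 144 on the persisting-effect reading.

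As an option, a baseline-adjusted comparison at T1, with λ = D²·N/(4(1 − ρ²)) and df2 = N − 3, has power of about 0.96 at 0.57 SD and ρ = 0.50 with 128 complete, and 0.91 with 102. It needs no additional recruitment.

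### The sample-size section pairs a partial η² of 0.02 with 95% power, but the formula that gives 95% uses a different effect-size scale; on the ANOVA's own scale, power is about 51%, and about 36% for the planned baseline-to-end-of-treatment comparison

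*Combined protocol and SAP*

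**What the plan says.** The Sample size calculation section (under METHODS) uses G*Power for F tests, with two arms measured "in 3 moments: (1) before the intervention", at the end of the intervention and 12 months after treatment ends. Because no earlier study offers a realistic estimate, the partial η² "was set a priori to assume a value of 0.02" and is called small. It is converted to a Cohen's f "value of 0.143". Alpha is 0.05, power "was set at 0.95", and the non-sphericity "correction was set to 1". A correlation between occasions is entered as well: "repeated measures was set at 0.50, according to general guidelines (56"). The section concludes: "Results showed that there is a 95% chance of correctly rejecting the null" hypothesis for the interaction, with 128 participants, 64 per arm. It does not say which of the software's effect-size definitions was used.

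Two other sections bear on this. Statistical analysis plans a repeated-measures ANOVA comparing the arms from baseline to treatment termination, then a within-group ANOVA over all occasions in the experimental arm only. Measures and Procedure confine the 6- and 12-month assessments to the experimental arm.

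**The concern.** Partial η² for a group-by-time interaction in a repeated-measures ANOVA is the interaction sum of squares divided by the sum of that and the within-person error sum of squares. The within-person error is already reduced by the correlation between occasions: its variance is proportional to 1 − ρ. An f derived from that partial η² therefore already carries the benefit of ρ = 0.50. Entering it into a formula that divides by 1 − ρ takes the benefit a second time, and that formula also scales by the number of occasions m where the ANOVA scale has m − 1.

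The size of the effect matters because the plan has no prior estimate, so calling the effect small is the only justification given for 128 participants. A reader would conclude that the trial is almost certain to detect an interaction of partial η² 0.02, and could read a null result as evidence against an effect of that size.

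**Working it through.** **Inputs** (Sample size calculation): partial η² = 0.02; N = 128; k = 2 arms; m = 3 occasions; ρ = 0.50; non-sphericity 1; α = 0.05.

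f² = 0.02/0.98 = 0.020408, so f = 0.1429. The stated 0.143 is right.

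**1. The plan's figure.** With f relative to the single-occasion (within-cell) SD:

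- λ = f²·N·m/(1 − ρ) = 0.020408 × 128 × 3/0.50 = 15.67
- df = (k − 1)(m − 1) = 2 and (N − k)(m − 1) = 252
- power = 0.951

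128 is the smallest even N that reaches 95%, so the plan's result is reproduced. A simulation of 4,000 trials gave 94.4%.

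**2. What that is on the ANOVA scale.** Partial η² = λ/(λ + df₂) = 15.67/(15.67 + 252) = 0.0586; with N(m − 1) = 256 in place of 252 it is 0.0577. Exactly 95% power needs λ = 15.63, which is 0.058. The effect with 95% power is therefore about three times the labelled 0.02.

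**3. Partial η² = 0.02 on the ANOVA scale, three occasions.**

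- λ = f²·(N − k)(m − 1) = 0.020408 × 252 = 5.14
- power = 0.511 (0.517 if N replaces N − k; simulation 0.517)

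**4. Where the gap comes from.** 15.67/5.14 = 3.05. This is 1/(1 − ρ) = 2, times m/(m − 1) = 1.5, times a trivial 128/126. Setting ρ = 0 in the formula of step 1 gives λ = 7.84 and power 0.70, so the correlation term explains only part of the fall from 0.95 to 0.51.

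**5. The planned between-arm test: two occasions, df 1 and 126.**

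With within-cell SD 1 and ρ = 0.50, the variance of a change score is 2(1 − ρ) = 1. A between-arm difference in change of δ with 64 per arm then gives λ = 32δ².

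| Effect | λ | δ (SD) | Power |
|---|---|---|---|
| f = 0.143 on single-occasion SD | 0.020408 × 128 × 2/0.50 = 10.45 | √(10.45/32) = 0.57 | 0.894 |
| ANOVA partial η² = 0.02 | 0.020408 × 126 = 2.57 | √(2.57/32) = 0.28 | 0.356 |

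For this test 80% power needs a partial η² of about 0.059, and 95% needs about 0.095.

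**6. Illustration only.** At N = 128, an observed partial η² of exactly 0.02 gives F(2, 252) = 0.020408 × 252/2 = 2.57, p = 0.078. Sample partial η² is biased upward (mean about 0.028 in simulation when the population value is 0.02), so this p-value does not measure power. Step 3 does.

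**The case against.** The strongest reply is that nothing was miscalculated: the conversion to f is right, 128 is what the stated inputs give, and 95% is valid for f = 0.143 relative to the within-cell SD. That stands. A reader might infer an arithmetic error in the software run, and the documents do not support that. The fault lies in the effect-size label, and it depends on reading 0.02 as the ANOVA's own partial η². That is the natural reading, because the planned analysis is a repeated-measures ANOVA and no other definition is given, but the section does not state it outright.

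A reader might also infer that counting the correlation twice explains the whole loss. It does not: removing that term alone leaves about 70%.

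A third tempting inference is that the trial must recruit about 380 participants. That is the N for 95% power if 0.02 was meant on the ANOVA scale for the three-occasion interaction. The documents do not establish that this effect is the one the trial must detect.

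It can further be said that the 51% concerns a test the trial will not run, since the waiting list has no assessment after two months. This is correct, and the restated power should therefore be for the two-occasion comparison. Changing the number of occasions alone would leave the label wrong, however.

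Finally, the planned Cohen's d values and 95% confidence intervals would show what a null result excludes. They limit the harm at reporting, but they do not correct the stated power.

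**Conclusion.** The point holds as a mismatch between the effect-size label and the formula. The statement that 128 participants give 95% power at partial η² 0.02 is not true on the scale of the planned ANOVA. Power there is about 51% for the three-occasion interaction described and about 36% for the baseline-to-end-of-treatment comparison, the only between-arm test planned. The 95% belongs to a three-occasion partial η² of about 0.058.

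These figures take the plan's own values as given: ρ = 0.50, sphericity, 1:1 allocation, and all 128 participants analysed. The 51% and 36% also require that 0.02 is the ANOVA's partial η². If f = 0.143 was meant on the single-occasion SD, the 95% stands for three occasions and becomes about 89% for two, but the partial η² label is then wrong. Under either reading the sentence needs correcting. The finding does not show that N = 128 is inadequate for a difference in change of about 0.57 SD.

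**What to change.** Keep N = 128 and restate the power in the Sample size calculation section:

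- State which effect-size definition was entered in the software.
- Remove the pairing of a small partial η² of 0.02 with 95% power.
- Report power for the group-by-time interaction from baseline to end of treatment: about 89% for f = 0.143 on the single-occasion SD (a 0.57 SD difference in change at ρ = 0.50), and about 36% for an ANOVA partial η² of 0.02 (0.28 SD). Add that 80% power is reached at a partial η² of about 0.059 and 95% at about 0.095.
- If the three-occasion figure is kept, give it as 95% at a partial η² of about 0.058 and about 51% at 0.02.

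The cost is a few sentences. No participants are added, and neither the analysis nor the procedures change. The downside is that the stated power becomes less favourable.
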